14.3.1. Evaluation of Response

Radiologic response will be assessed after immunotherapy completion – prior to locoregional therapy initiation using RECIST 1.1 and/or mRECIST. Pathologic response will be assessed in the explanted liver. Recurrence-free survival and overall survival will be assessed for five years.

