Study Design: ESR-20-21010 is a single-arm, open-label, Phase II, multicenter clinical trial designed to evaluate the safety and efficacy of durvalumab and tremelimumab for the treatment of hepatocellular carcinoma (HCC) patients who have cirrhosis or portal hypertension and are listed for a liver transplant. The key eligibility requirements include HCC, Child-Pugh score of up to 7, and ECOG PS of 0 or 1. Patients will be treated with the immunotherapy combination for up to 4 months. After a minimum 28 day gap following the final durvalumab dose, they will undergo locoregional therapy per institutional standards. Eventually, after a minimum 72-day gap from the end of immunotherapy, they will undergo liver transplant.

The primary endpoint is proportion of patients experiencing post-transplant rejection, graft loss, death, or loss to follow up (within 30 days of transplant). A total of 30 patients are to be enrolled, to allow at least 20 transplants for adequate primary endpoint analysis. An interim analysis after 10 patients will be performed to ensure safety. If there are untoward safety signals, study modification/discontinuation will be taken into consideration by the UCCC DSMB, investigators, the sponsor-investigator and AstraZeneca during the study and at interim analysis.

Number of Centers: 3

Number of Patients: 30

Study Population: HCC patients who have cirrhosis or portal hypertension and are listed for a liver transplant.

Inclusion Criteria:
 
 1. Hepatocellular carcinoma, diagnosed either by biopsy or by combination of cirrhosis and imaging criteria (contrast-enhanced CT or MRI) 2. Tumor confined to liver (no evidence of extrahepatic disease), with no macrovascular invasion 3. Patient evaluated by institutional Liver Transplant team and deemed eligible for transplant 4. Measurable disease by RECIST 1.1 5. No prior therapy for HCC 6. Adult patient (Age ≥ 18) 7. ECOG = 0 or 1 Child-Pugh Score = 5, 6, or 7 8. Creatinine < 1.5 ULN 9. Body weight > 30 kg

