 - Two 10 mL EDTA tubes collected 4 weeks post-transplant +/- 3 days.
- k. Per correlative section #9. Stool sample must be collected after eligibility is confirmed but prior to I/O.
- l. tissue will be sequenced by CARIS as a SOC process.
- m. The post-I/O safety eval must occur 28 days following the final dose of durvalumab.
- n. A minimum 28-day gap after I/O before beginning L/R is required. L/R therapy can continue/repeat per treating physician discretion.
- o. At least after 72 days following final dose of durvalumab.
- p. Every 6 months +/- 1 month for standard of care, survival and disease progression data may be abstracted from this imaging.
- q. Transplant graft rejection data will be collected at 30 days after transplant and at 3 months and 6 months during long term follow-up.
- r. Subjects should be contacted by telephone or seen in clinic every 3 months from the end of I/O for the first year then every 6 months for up to 5 years to assess for survival status. Time-points noted under L/R Therapy, Transplant, and Post-op are intended to indicate that depending on the timing of each these may contain q3month time-points from I/O at which this data collection should occur.
- s. Tumor assessments must include measures for either RECIST 1.1 or mRECIST or both if institutionally allowed.
- t. 30-day post-transplant SOC visit in oncology with a +/- 7 day window to include medical history and physical.

Table of Contents

1.	Protocol Synopsis	2
2.	SCHEMA 5	
3.	STUDY CALENDAR	6
4.	abbreviations and definition of terms	10
5.	OBJECTIVES 14	
5.1.	Primary Objectives.....	14
5.2.	Secondary Objectives.....	14
5.3.	Exploratory Objectives	14
6.	BACKGROUND	14
6.1.	Immunotherapy Background	14
6.2.	Durvalumab (MEDI4736) Background	15
6.3.	Tremelimumab Background	16
6.4.	Durvalumab in combination with tremelimumab	16
6.5.	Durvalumab + tremelimumab combination therapy dose rationale.....	17
6.6.	Hepatocellular Carcinoma Background.....	18
6.7.	Correlative Studies Background	19
7.	PATIENT SELECTION: Eligibility.....	20
7.1.	Inclusion Criteria	20
7.2.	Exclusion Criteria	21
7.3.	Inclusion of Women and Minorities	23
8.	REGISTRATION PROCEDURES	23
8.1.	Assignment of Screening and Subject Numbers.....	23
8.2.	Patient Screening	24
8.3.	Patient Registration.....	24
8.4.	General Guidelines.....	24
9.	BIOMARKER, CORRELATIVE, AND SPECIAL STUDIES	25
9.1.	Biomarker Plan	25
9.2.	Exploratory/Ancillary Correlative Studies	27
10.	TREATMENT PLAN.....	28

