5.2. Secondary Objectives

1. To assess the safety of immunotherapy for treatment of HCC in patients listed for a liver transplant, with respect to adverse events during treatment, and graft loss and mortality rates.
2. To assess the efficacy of immunotherapy for treatment of HCC in patients listed for a liver transplant, with respect to radiologic and pathologic responses, and survival outcomes.

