10.2. Durvalumab + tremelimumab combination therapy

Tremelimumab 300 mg via IV infusion x 1 dose on day 1 of the first cycle, plus durvalumab 1500 mg via IV infusion Q4W starting on day 1, for up to a maximum of 4 months (5 doses of durvalumab). N.B If a patient's weight falls to 30kg or below (≤ 30 kg), then the patient should receive weight-based dosing equivalent to 20 mg/kg of durvalumab Q4W after consultation between the investigator and study physician, until the weight improves to above 30 kg (>30 kg), at which point the patient should start receiving the fixed dosing of durvalumab 1500 mg Q4W).

Patients will be treated with the immunotherapy combination for up to 4 months. After a minimum 28 day gap following the final durvalumab dose, they will undergo locoregional therapy per institutional standards. Eventually, after a minimum 72-day gap from the end of immunotherapy, they will undergo liver transplant.

Tremelimumab will be administered first over 1 hour; the durvalumab infusion will then be started approximately 1 hour after the end of the tremelimumab infusion to allow for a 1 hour observation

period. Standard infusion time for each is 1 hour, however if there are interruptions, the total allowed time must not exceed 4 hours from the start of infusion at room temperature per infusion.

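### Pathologic response is listed as immunotherapy efficacy but is read after locoregional therapy with no control arm, so it describes the combined sequence; its denominator is also not stated

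*Combined protocol and SAP*

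**What the plan says.** Section 5.2 sets the objective: "To assess the efficacy of immunotherapy for treatment of HCC in patients listed for a liver transplant, with respect to radiologic and pathologic responses". The synopsis carries the same objective. Section 14.3.1 fixes the specimen: "Pathologic response will be assessed in the explanted liver".

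Section 10.2 gives the treatment order. First: "After a minimum 28 day gap following the final durvalumab dose, they will undergo locoregional therapy per institutional standards". Then: "Eventually, after a minimum 72-day gap from the end of immunotherapy, they will undergo liver transplant". The Study Calendar leaves the type of locoregional therapy to the treating physician (footnote c, which gives TACE and SIRT as examples) and leaves its amount open as well (footnote n): "L/R therapy can continue/repeat per treating physician discretion". The synopsis states the design: "ESR-20-21010 is a single-arm, open-label, Phase II, multicenter clinical trial".

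Radiologic response is handled differently. Section 14.3.1 places it after immunotherapy and "prior to locoregional therapy initiation using RECIST 1.1 and/or mRECIST".

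On analysis, section 14.3 says only that the radiologic and pathologic response rates are to be treated as proportions. It names no denominator for pathologic response and no rule for patients without an explant. The one definition of a response-evaluable patient, in section 16.1, belongs to the imaging criteria and does not mention pathology.

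**The concern.** The objective asks what immunotherapy does to the tumour. The explant shows what is left after immunotherapy and then one or more locoregional treatments, which are themselves directed at the tumour. Sections 5.2 and 14.3.1 pair this endpoint with radiologic response under one immunotherapy-efficacy objective, yet only the radiologic reading is timed to exclude the second treatment.

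A second question concerns who is counted. An explant exists only for a patient who reaches transplant. The trial enrols 30 to obtain at least 20 transplants, so up to about a third of patients may have no pathologic reading.

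Section 6.6 presents this trial as the safety step before a larger efficacy study. A pathologic response rate reported under the present label could be carried into planning that study as immunotherapy activity.

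**Working it through.** The plan gives no expected rate, sample size or interval for pathologic response, so there is no stated figure to reproduce. Response counts and rates below are assumptions used to show size.

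**1. Attribution**

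Let pI be the proportion of explants that would show response from immunotherapy alone, and pL the proportion of the remainder in which locoregional therapy produces response. Then

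observed rate = pI + (1 − pI) × pL.

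- pI = 0, pL from 10% to 50%: the observed rate is 10% to 50%, with no immunotherapy effect at all.
- pI = 20%, pL from 10% to 50%: 0.20 + 0.80 × 0.10 = 28%, up to 0.20 + 0.80 × 0.50 = 60%.
- An observed 28% fits pI = 20% with pL = 10%; it fits pI = 10% with pL = 20% (0.10 + 0.90 × 0.20 = 0.28); and it fits pI = 0 with pL = 28%.

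One observed number cannot determine two unknowns. No patient is planned to reach explant without locoregional therapy, and there is no comparator to supply pL.

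**2. Denominator**

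Inputs: 30 enrolled and at least 20 transplanted (section 14.2); 25 transplants as the other case considered (section 14.1); 25% to 35% historically missing transplant because of progression (section 6.6). That history implies 30 × 0.75 = 22.5 to 30 × 0.65 = 19.5 transplants, in line with the plan's minimum of 20.

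Take all 30 as treated and count no explant as non-response. For x responders among T explants, the ratio of the explant-only rate to the all-treated rate is (x/T) ÷ (x/30) = 30/T, whatever x is.

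| Transplants T | Ratio 30/T | Explant-only rate, x = 6 assumed (exact 95% CI) | All-treated rate, 6/30 (exact 95% CI) |
|---|---|---|---|
| 20 | 1.50 | 30.0% (11.9 to 54.3) | 20.0% (7.7 to 38.6) |
| 22 | 1.36 | 27.3% (10.7 to 50.2) | 20.0% (7.7 to 38.6) |
| 25 | 1.20 | 24.0% (9.4 to 45.1) | 20.0% (7.7 to 38.6) |

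**3. How certain is the direction?**

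Counting a missing explant as non-response is a convention. With 6 responders among 20 explants and the other 10 patients left unknown, the all-treated rate lies between 6/30 = 20.0% and 16/30 = 53.3%. The explant-only 30.0% sits inside that range. It overstates the all-treated rate if fewer than 3 of the 10 would have shown response, and understates it if more than 3 would have. Section 6.6 attributes missed transplants to progression, which makes overstatement the likelier case. Section 14.2 also foresees patients missing transplant through immunotherapy toxicity, which by itself says nothing about tumour response.

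**The case against.** The strongest reply is that nothing is hidden. The sequence is set out in the synopsis and in section 10.2, pathologic response is secondary and descriptive with no threshold or decision rule, and an immunotherapy-only readout already exists in the pre-locoregional imaging. Those facts stand and they limit the severity. They do not settle the labelling, because section 5.2 still names pathologic response as evidence on immunotherapy.

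A reader might infer three stronger things that the documents do not support.

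- **That the rate is inflated by its denominator.** Section 14.3 states no denominator, so the supported finding is that it is unspecified. A proportion clearly labelled as being among explants is valid for that group, and the research hypothesis in the synopsis does concern patients undergoing transplant, although objective 5.2 concerns those listed.
- **That patients who miss transplant are dropped.** Sections 10.6 and 10.7 keep them in follow-up, section 11.8 gives them imaging every six months, and they remain available for radiologic response and survival. They lack only the specimen.
- **That the trial's efficacy conclusion would be wrong.** The plan sets no rule that turns pathologic response into a conclusion. The risk lies in how the rate is described.

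Two related observations are fair. Recurrence-free and overall survival sit under the same objective and also follow the whole sequence. And the plan gives no definition of pathologic response, such as a necrosis or viable-tumour cut-off, so the rate cannot be calculated under either denominator until one is supplied.

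**Conclusion.** The attribution point holds on the text alone and needs no assumed figure: every planned explant follows unstandardised, repeatable locoregional therapy in a single-arm trial, so pathologic response measures the sequence and cannot be assigned to immunotherapy. The 10% to 50% illustration rests on an assumed locoregional response rate.

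The denominator point holds as an omission. If explants alone are counted, the rate is conditional on reaching transplant and is 1.2 times (25 transplants) to 1.5 times (20 transplants) the all-treated rate, assuming all 30 are treated and no explant counts as non-response. Upward bias is likely from the plan's own account of why patients miss transplant, but it is not established.

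This should be corrected before analysis. It does not touch the primary safety endpoint.

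**What to change.** In sections 5.2, 14.3 and 14.3.1, and in the matching synopsis text:

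1. Describe pathologic response as the outcome of immunotherapy followed by locoregional therapy, among explanted patients.
2. Report that proportion with an exact 95% interval, beside the proportion over all treated patients with its own exact interval. Count no explant as non-response and say that this is a conservative convention.
3. Base any conclusion about response to immunotherapy alone on the radiologic response measured before locoregional therapy starts. Sections 11.8 and 16.1 ask for confirmation scans about four weeks after a first response, which could fall after locoregional therapy has begun, so the text should specify pre-locoregional imaging.

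A breakdown by number of locoregional sessions is not recommended. With about 20 explants the cells would be very small, and because repetition is discretionary, the session count may itself reflect poor response.

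The cost is a wording change that reaches a protocol objective, one extra table row, a lower all-treated rate and a narrower claim. No treatment, visit or sample size changes.

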15. ADVERSE EVENTS: KNOWN RISKS AND REPORTING REQUIREMENTS

15.1. Overall Risks

Monoclonal antibodies directed against immune checkpoint proteins, such as programmed cell death ligand 1 (PD-L1) as well as those directed against programmed cell death-1 (PD-1) or cytotoxic T-lymphocyte antigen-4 (CTLA-4), aim to boost endogenous immune responses directed against tumor cells. By stimulating the immune system however, there is the potential for adverse effects on other tissues.

Most adverse drug reactions seen with the immune checkpoint inhibitor class of agents are thought to be due to the effects of inflammatory cells on specific tissues. These risks are generally events with a potential inflammatory or immune mediated mechanism and which may require more frequent monitoring and/or unique interventions such as immunosuppressants and/or endocrine therapy. These immune mediated effects, can occur in nearly any organ system, and are most commonly seen as gastrointestinal AEs such as colitis and diarrhea, pneumonitis/interstitial lung disease (ILD), hepatic AEs such as hepatitis and liver enzyme elevations, skin events such as rash and dermatitis and endocrinopathies including hypo- and hyper-thyroidism.

15.2. Known Risks of Durvalumab

Risks with durvalumab include, but are not limited to, cough/productive cough, diarrhea/colitis, pneumonitis, interstitial lung disease, dysphonia, alanine aminotransferase increased/aspartate aminotransferase increased, abdominal pain, endocrinopathies (hypo- and hyper-thyroidism, type I diabetes mellitus (which may present as diabetic ketoacidosis), Diabetes Insipidus, hypophysitis/hypopituitarism and adrenal insufficiency), thyroiditis, hepatitis/increases in transaminases, nephritis/increases in creatinine, night sweats, dysuria, pyrexia, oedema peripheral, upper respiratory tract infections, pneumonia, oral candidiasis, dental and oral soft tissue infections, influenza, myalgia, pancreatitis/increases in amylase and lipase, rash/pruritus/dermatitis (including pemphigoid), myocarditis, myositis/polymyositis, immune-mediated arthritis, myasthenia gravis, Guillain-Barré syndrome, infusion-related reaction, immune thrombocytopenia, noninfective encephalitis, and uveitis. Potential risk for durvalumab monotherapy includes subcutaneous injection site reaction, hypersensitivity reactions including

anaphylaxis and allergic reaction, cytokine release syndrome, and immunogenicity. Other rare or less frequent inflammatory events including neuropathy/neuromuscular toxicities vasculitis, non-infectious meningitis, psoriasis. For information on all identified and potential risks with durvalumab please always refer to the current version of the durvalumab IB.

In monotherapy clinical studies AEs (all grades) reported very commonly ($\geq 15\%$ of patients) are fatigue, nausea, decreased appetite, dyspnea, cough, constipation, diarrhea, vomiting, back pain, pyrexia, asthenia, anemia, arthralgia, peripheral edema, headache, rash, and pruritus. Approximately 9.4% of patients experienced an AE that resulted in permanent discontinuation of durvalumab and approximately 6.6 % of patients experienced an SAE that was considered treatment-related by the study investigator.

The majority of treatment-related AEs were manageable with dose delays, symptomatic treatment, and in the case of events suspected to have an immune basis, the use of established treatment guidelines for immune-mediated toxicity (please see Appendix 1) A detailed summary of durvalumab monotherapy AE data can be found in the current version of the durvalumab IB.

15.3. Known Risks of Tremelimumab

Risks with tremelimumab monotherapy include, but are not limited to, GI effects (colitis, diarrhoea, enterocolitis and intestinal perforation), endocrine disorders (hypo and hyperthyroidism, hypophysitis and adrenal insufficiency), skin effects (rash, and pruritus), elevations in lipase and amylase and clinical manifestations of pancreatitis, other gastrointestinal events e.g. ulcerative colitis, dehydration, nausea and vomiting; hepatic events including hepatitis, and liver enzyme elevations; pneumonitis and ILD; nervous system events including encephalitis, peripheral motor and sensory neuropathies, Guillain-Barre and proximal muscle weakness; cytopenias including thrombocytopenia, anemia and neutropenia; infusion-related reactions, anaphylaxis, and allergic reactions; renal events including renal failure, acute kidney injury, nephritis, nephrotic syndrome, autoimmune nephritis and electrolyte abnormalities such as hypokalemia; autoimmune diseases including autoimmune arthritis, Sjogren's syndrome and giant cell temporal arteritis; hyperglycemia and diabetes mellitus; and pyrexia. For information on all identified and potential risks with tremelimumab please always refer to the current version of the tremelimumab IB.

Using pooled data from monotherapy clinical studies AEs (all grades) reported very commonly ($\geq 10\%$ of patients) were diarrhea, nausea, fatigue, pruritus, decreased appetite, rash, vomiting, dyspnoea, constipation, cough, pyrexia, abdominal pain, decreased weight, headache, asthenia, and anaemia. Approximately 16% of patients experienced an AE that resulted in permanent discontinuation of tremelimumab and approximately 45% of patients experienced an SAE. Further information on these risks can be found in the current version of the tremelimumab IB. A detailed summary of tremelimumab monotherapy AE data can be found in the current version of the tremelimumab IB.

15.4. Known Risks of Durvalumab + Tremelimumab

The safety of durvalumab + tremelimumab combination therapy was initially evaluated in the

ongoing dose escalation and dose expansion Study 006, in patients with NSCLC, and is being studied in a number of other ongoing clinical trials, in a number of different indications, and has to date shown a manageable safety and tolerability profile.

The types of risks with the combination of durvalumab + tremelimumab (based on an equivalent durvalumab dose of 20mg/kg and a tremelimumab dose of 1mg/kg) are similar to those for durvalumab and tremelimumab monotherapy. Emerging data from study 006, other studies evaluating the combination, and from combinations of other agents in the same class indicate an increased frequency and/or severity of some of these immune-mediated toxicities. For information on all identified and potential risks with the durvalumab+tremelimumab combination please always refer to the current version of the durvalumab IB.

In durvalumab+tremelimumab combination studies at the dose of durvalumab 20mg/kg and tremelimumab 1mg/kg AEs (all grades) reported very commonly ($\geq 15\%$ of patients) are diarrhoea, fatigue, decreased appetite, nausea, pruritus, constipation, and anaemia; AEs reported in $\geq 5\%$ of patients that were considered by the investigator as treatment-related were diarrhoea, pruritus, fatigue, rash, hypothyroidism, decreased appetite, nausea, asthenia, and hyperthyroidism. Known risks of combination therapy includes amylase increased, lipase increased, pancreatitis and noninfective encephalitis. Potential risks of the combination treatment include pulmonary embolism and subcutaneous injection site reaction. Approximately 17% of patients experienced an AE that resulted in permanent discontinuation of study drug and approximately 18% of patients experienced an SAE that was considered to be related to durvalumab and tremelimumab by the study investigator. A detailed summary of durvalumab + tremelimumab combination AE data can be found in the current version of the durvalumab IB.

15.5. Adverse Events Definition

An adverse event is defined as the development of an undesirable medical condition (other than progression of the malignancy under evaluation) or the deterioration of a pre-existing medical condition following or during exposure to a pharmaceutical product, whether or not considered causally related to the product. An undesirable medical condition can be symptoms (e.g., nausea, chest pain), signs (e.g., tachycardia, enlarged liver) or the abnormal results of an investigation (e.g., laboratory findings, electrocardiogram). In clinical studies, an AE can include an undesirable medical condition occurring at any time, including run-in or washout periods, even if no study treatment has been administered

The severity (grade) of an adverse event may be determined by a study coordinator using the CTCAE version 5.

The causal relationship (attribution) to study drug/device/intervention is determined by a study physician and should be used to assess all adverse events (AE). The casual relationship can be one of the following:

1. Unrelated – The AE is clearly NOT related to the study intervention
2. Unlikely – The AE is doubtfully related to the study intervention
3. Possible – The AE may be related to the study intervention

4. Probable – The AE is likely related to the study intervention
5. Definite – The AE is clearly related to the study intervention

The expectedness of the occurrence of an adverse event is determined by a study physician and should be used to help determine whether prompt reporting requirements to regulatory authorities (IRB, FDA etc...) are required (such as when the AE is an SAE).

1. Expected – An adverse event is expected if it is described as an anticipated risk in the Investigator Brochure (IB) and described within this protocol as a known adverse event.
2. Unexpected – If an adverse event is not described within the IB, or within this protocol or consent form as an expected risk to subjects then the AE will be considered to be unexpected.

Adverse events can be spontaneously reported or elicited during open-ended questioning, examination, or evaluation of a subject.

